#### **SUMMARY**

This open-label, randomized parallel group clinical trial will study subcutaneous depot medroxyprogesterone acetate (DMPA sc) self-administration at two Planned Parenthood affiliates serving diverse patient populations. A total of 400 female patients (ages 15–44) requesting DMPA will be randomized to either self-administration of DMPA sc or clinic administration (usual care) in a 1:1 allocation. Subjects will be followed for one year to compare method continuation rates and patient satisfaction between arms. All subjects will receive reminders when their next injection is due. Follow-up surveys will be conducted at 6 and 12 months via secure email, phone, text messaging, or a combination to increase response rate. Adherence will be monitored by subject self-report and study outcomes will be ascertained by self-report and medical record review.

The primary study outcome is DMPA continuation at one year by self-report in both study arms. Secondary outcomes include patient-reported satisfaction with treatment; satisfaction with home use; and costs associated with contraceptive care. We hypothesize higher continuation rates among self-injection users compared to patients who receive standard care and have sufficient statistical power to detect an estimated 13% difference (80% power; one-sided  $\alpha$ =0.05; allowing for 15% loss-to-follow-up). The study will include some minors (ages 15–17) — a population at high risk of unintended pregnancy — due to limited information available from previous studies (Williams et al. 2013). The proposed trial will be substantially larger than prior studies of self-administration.

The study is funded by a private grant from the Tara Health Foundation, with additional support requested from Pfizer in the form of one-year drug supply for all randomized study participants.

#### STUDY DESCRIPTION

### **Rationale**

In the United States nearly half of all pregnancies are unintended and one-third are mistimed (Finer & Zolna 2011). Higher rates of unintended pregnancy persist in many of the subpopulations served by Planned Parenthood, including younger women ages 18–24, minorities, and low-income women. The most effective way to reduce unintended pregnancy is to increase consistent use of effective contraceptive methods. The best contraceptive method for any individual woman is the method that she is most likely to use consistently — the method that works best for her.

The National Survey of Family Growth (NSFG) estimates that approximately 4% of contraceptive users ages 15–44 in the U.S. rely on injectable contraception. This amounts to nearly 1.5 million women (Guttmacher Institute 2014). Among Planned Parenthood clients, use of injectable contraception is higher. In 2013, approximately 12% of female contraceptive clients were relying on DMPA — roughly 250,000 women and adolescents.

Recent studies demonstrate that DMPA self-injection is safe, effective, feasible, and acceptable to patients (Beasley et al. 2014; Prabhakaran & Sweet 2012; Cameron et al. 2012); however, we do not know whether self-administration results in better contraceptive continuation. Previous studies have been too small to have sufficient statistical power to detect clinically important differences between groups.

This study will build upon the strengths of prior studies to generate additional evidence on continuation of DMPA to assess whether this practice can increase continuation for both adult women and adolescents by removing barriers to care.

This study will make a contribution to the existing evidence on feasibility, satisfaction, and continuation of DMPA, with potential to immediately affect practice. If the findings are positive, the study will lead to a change to the *PPFA Medical Standards and Guidelines*, improving access and care for thousands of Planned Parenthood patients across the country. Study results will also likely influence practice outside of Planned Parenthood settings.

# **Objectives and Hypotheses**

The primary study objective is to compare one-year method continuation rates between patients who self-administer DMPA sc outside of the clinic setting and those who receive in-clinic administration of DMPA sc. Secondary objectives are to: confirm the feasibility and acceptability of self-injection among adult and adolescent DMPA users; compare method satisfaction rates between patients who self-administer and those who receive in-clinic injections; and compare costs associated with contraceptive care across both groups.

Primary study outcome: DMPA sc continuation at one year by self-report in both the self- and clinic administration arms.

Secondary study outcomes: Patient-reported satisfaction with treatment; satisfaction with home use; cost differentials.

Primary research question: Will allowing for self-administration of DMPA sc outside of the clinic setting result in increased method continuation rates at 6 and 12 months?

## Secondary research questions:

- Do adult and adolescents patients report that self-administration of DMPA sc is a feasible and satisfactory alternative to clinic administration of DMPA sc?
- What are the cost-related implications of self-administration of DMPA sc compared to clinic administration for patients, providers, and payers?

Primary Hypothesis: We hypothesize higher continuation rates among self-administration users compared to patients who receive in-clinic administration.

- Independent variable: Self-administered DMPA sc versus clinic administered DMPA sc.
- Dependent variables: DMPA continuation rates at 6 and 12 months, defined as having received 3 contraceptive injections by 26 weeks post-enrollment and 4 injections by 42 weeks post-enrollment.

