#### **Previous Similar Studies**

Prior studies show that DMPA self-injection is effective, feasible, and acceptable to patients. Most recently, Beasley et al. (2014) conducted a randomized trial with 137 women to evaluate the feasibility, acceptability, and continuation of self-administration of DMPA sc versus clinical administration, and to confirm the therapeutic effect using trough serum levels. They found that 90 out of 91 women randomized to the self-administration group were able to correctly self-inject. Continuation rates were somewhat higher in the self-administration group (71% vs. 63%); however, this difference was not statistically significant (p=0.47) and the study did not have adequate statistical power to detect a difference of this magnitude (i.e., 8%). All of the women who reported continuous use of DMPA had serum levels in the therapeutic range, confirming the ability of women to learn self-administration, continue it successfully at home, and reliably self-report such use. This study required repeated visits in both groups to assess serum levels and therefore involved significant intervention with both groups, potentially attenuating the difference between groups.

A non-randomized study of 120 women by Cameron et al. (2012) found that 80% of self-injections were given on time, and that no injections were given beyond the acceptable 14-week interval. The authors also found that continuation rates were higher in the self-administration group than the clinic

administration group (88% vs. 72%); however, this difference was not statistically significant and again the study did not have statistical power to detect such a difference. Cameron et al. found that the majority of women who wanted to use Depo at home were able to do so; however, 20% experienced some difficulty with one or more of the self-injections due to either resistance to the medication passing through the needle (17%) or the needle detaching from the syringe (2%).

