## **Study Procedures**

Once enrolled, all participants will be seen by a clinician. Based on study assignment, subjects will either be taught to self-inject or will be administered DMPA by qualified clinic personnel. Nurses who dispense DMPA sc (regardless of study arm) will record the name of each subject receiving the medication, her chart number, and the lot number of the medication distributed to the patient on a Study Drug Distribution Log to be maintained in the pharmacy.

Subjects who are randomized to self-administration will be taught self-administration by a clinic nurse (or other qualified personnel) following an instructions sheet based on the drug packaging insert. If willing, subjects will then self-administer DMPA sc under nurse supervision. Subjects who are able to correctly self-administer DMPA sc as assessed by the supervising nurse and who are interested in continued home self-administration will then be provided medication (3 doses of DMPA sc), a self-administration kit (includes alcohol swabs, cotton pads, bandages, mini sharps disposal container), and instructions to do so for the subsequent 3 injections along with a small calendar showing the appropriate dates for injection. The calendar will also indicate when the subject will be asked to complete each of the 2 follow-up surveys.

Subjects who are uninterested in self-administration either after the educational session or after correctly self-administering medication in the office will be permitted to crossover to the clinic administration group and remain in the study. They will be re-assigned to the clinic administration group and be followed accordingly. Subjects will not be told ahead of time that they can opt out of their randomization assignment and remain in the study to discourage enrollment of subjects who are not actually willing to be in the self-administration group.

Subjects new to DMPA will be started using the QuickStart protocol (per Planned Parenthood routine practice) and will be instructed to perform a provided pregnancy test in four weeks and report the result to clinic to be documented by the Research Coordinator in the subject correspondence log. Subjects who did not provide the result of the pregnancy test will be contacted by study staff to be documented in the correspondence log.

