## **Follow-Up Procedures**

Subjects will either return to the enrollment clinic or perform self-injection every 12–14 weeks, depending on study arm. The appropriate date for injection will be indicated on the subject's instructions for injection/calendar. All subjects (both arms) will receive reminder emails and/or text messages two weeks *before* their next injection is due. Reminders will be generated by PPFA investigators using the secure Qualtrics electronic survey platform which enables programmable email and text message communications.

If a subject is uncertain if she was able to administer the entire dose of DMPA she should return to the enrollment clinic and have a complete dose administered. The event will be recorded and reported to the Pfizer Quality Complaints department. These subjects may continue to receive injections at the enrollment clinic or return to self-administration; this will be documented by the site Research Coordinator.

Subjects who are uncomfortable with self-injection at any point in the study may return to the enrollment clinic to receive their injection per usual clinic protocol (i.e. study arm crossover to usual care will be permitted and tracked). They will be asked to complete all surveys and follow-up activities and be included in the clinic administration group. Subjects should continue to complete all surveys regardless of the location at which she receives her injection.

Crossover will be permitted from the self-administration arm to the clinic administration arm only. Any subject crossover will be documented by the Research Coordinator with the subjects' ID number to permit later assessment of crossover and ITT analyses.

The Research Coordinator will provide the Principal Investigator with a list of subjects enrolled each month so that PPFA investigators can complete the appropriate follow up. Approximately two weeks after subjects' target injection dates, follow-up surveys will be emailed by PPFA investigators to all participants. If no survey is completed by 16 weeks after previous injection, study staff will contact the subject twice and at her alternate contact to remind them to complete the survey whether they administered DMPA or not.

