### **Data Analysis**

The Principal Investigator and Data Manager have access to a secure computer with Excel, SPSS, and STATA software. Analyses will be performed on an intent-to-treat basis. We will perform descriptive analyses of demographic variables to assess the success of randomization and characterize the study population. Chi-square and t-test analyses will be used to compare proportions and mean differences between groups. The primary analysis will compare DMPA continuation rates between the intervention and control groups at 6 and 12 months. Cox proportional hazards regression analyses will be used for survival analysis. Secondary analyses will compare satisfaction scores and time/money spent on contracepting behaviors between the two groups.

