#### **Number of Subjects and Statistical Power**

The study sites will enroll a combined total N of 400 women. Individuals will be randomized to self-administration or clinic administration with a 1:1 allocation, such that 200 women will be randomized to self-injection, and 200 women to clinic administration. A 15% loss to follow-up rate will yield completed surveys from approximately 340 participants. Based on previous studies, we hypothesize greater continuation rates among self-injection users compared to patients who receive standard care and have sufficient statistical power to detect a difference of 13% or greater. While we will ask subjects about unintended pregnancies, given the high efficacy of DMPA, we will not have statistical power detect a difference between groups.

Given the primary study hypothesis that increased accessibility to DMPA through self-administration will result in higher method continuation rates and the results of prior studies, we estimate that the intervention group will have a 70% continuation rate at 12 months and the control group a 57% continuation rate. With a one-sided  $\alpha$ =0.05 and a  $\beta$ =0.80 and accounting for an approximately 15% dropout rate, completed follow-up from 338 subjects will be sufficient to detect the hypothesized difference. The study is not designed to detect statistically significant differences between adolescents and adults, or between method initiators and continuers.

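### The 6-month continuation cut-off of 26 weeks falls in the middle of the on-schedule window for injection 3, so women who keep to the 12–14-week interval can be scored as discontinued

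*Combined protocol and SAP*

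**What the plan says.** Under the Primary Hypothesis (section Secondary research questions), the dependent variables are the 6- and 12-month continuation rates, "defined as having received 3 contraceptive injections by 26 weeks post-enrollment and 4 injections by 42 weeks post-enrollment".

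Study Procedures has the first injection given at the enrollment visit. Women who will self-inject then receive three more doses, with "instructions to do so for the subsequent 3 injections along with a small calendar showing the appropriate dates for injection". Follow-Up Procedures sets the interval for both arms: women either return to the clinic or "perform self-injection every 12–14 weeks, depending on study arm".

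The 6-month rate has a prominent place. The primary research question asks whether self-administration will "result in increased method continuation rates at 6 and 12 months", and Data Analysis states: "The primary analysis will compare DMPA continuation rates between the intervention and control groups at 6 and 12 months". The named primary outcome in Objectives and Hypotheses is nevertheless continuation at one year, and the sample size rests on 12-month rates only.

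**The concern.** The two cut-offs stand in one sentence but follow different rules. The later one allows every interval to run to the 14-week limit; the earlier one allows an average of only 13 weeks. No section gives a grace period or a reason for the tighter limit.

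A woman whose first two intervals total more than 26 and up to 28 weeks has followed the schedule, yet counts as having stopped at 6 months. She can still count as a continuer at 12 months. The rule therefore lowers the 6-month rates in both arms, shrinks the absolute difference between them and costs power. It can also produce a 6-month rate below the 12-month rate, which is impossible for true cumulative continuation and would be visible in any report.

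**Working it through.** **Inputs from the protocol.** Injection 1 at week 0 and three to follow (Study Procedures); interval 12–14 weeks (Follow-Up Procedures); cut-offs of 26 and 42 weeks (Primary Hypothesis); 70% versus 57% at 12 months, one-sided α = 0.05, 80% power, 338 completers and 15% loss (Number of Subjects and Statistical Power, Study Design).

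**1. The plan's own figure.** Two-proportion test with pooled variance, no continuity correction:

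n per arm = [z_α√(2p̄q̄) + z_β√(p₁q₁ + p₂q₂)]² / d²

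With p̄ = 0.635 and d = 0.13: (1.645 × 0.681 + 0.842 × 0.675)² / 0.0169 ≈ 168.5, so 169 per arm and 338 in total, as stated. 338 / 0.85 gives 398, against 400 planned. Power with 169 per arm is 80%.

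**2. On-schedule windows.** Injection k is on schedule from (k − 1) × 12 to (k − 1) × 14 weeks.

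| Injection | On-schedule weeks | Cut-off | Position of cut-off |
|---|---|---|---|
| 3 | 24–28 | 26 = 2 × 13 | midpoint |
| 4 | 36–42 | 42 = 3 × 14 | end |

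**3. Share misclassified at 6 months.** This is P(first two intervals total more than 26 weeks). The documents do not give it. It is 0% if every interval is 13 weeks or less and 100% if every interval is 14. Assuming two independent intervals on 12–14 weeks:

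- triangular, peak at 12: 1/6 = 17%
- uniform, or triangular with peak at 13: 50%
- triangular, peak at 14: 5/6 = 83%

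In every case 0% have injection 4 after week 42.

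**4. Effect on the 6-month comparison.** The plan gives no 6-month rates. Assuming equal drop-out at each of the three steps to injection 4, the true injection-3 rates are 0.70^(2/3) = 78.8% and 0.57^(2/3) = 68.7%. If a share m is misclassified equally in both arms, both rates are multiplied by (1 − m). Power = Φ{[d√n − z_α√(2p̄q̄)] / √(p₁q₁ + p₂q₂)} with n = 169 per arm:

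| m | Self-administration | Clinic | Power |
|---|---|---|---|
| 0 | 78.8% | 68.7% | 68% |
| 17% | 65.7% | 57.3% | 48% |
| 50% | 39.4% | 34.4% | 25% |
| 83% | 13.1% | 11.5% | 12% |

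**5. When the 6-month rate drops below the 12-month rate.** Self-administration: m > 1 − 0.70/0.788 = 11%. Clinic: m > 1 − 0.57/0.687 = 17%.

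**6. Survey timing.** Surveys go out about two weeks after "target injection dates, follow-up surveys will be emailed by PPFA investigators to all participants". For injection 3 that is week 2 × target + 2: week 26, 28 or 30 for a target interval of 12, 13 or 14 weeks. The target is not stated. Only a 12-week target puts the survey before the window closes at week 28.

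**The case against.** The arithmetic of the windows is not in dispute. The case on the other side concerns weight and remedy.

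- **The named primary outcome is untouched.** It is continuation at one year, and the 6-month comparison was never powered. This stands and limits the severity. The 6-month rate is still in the primary research question, the dependent variables and the primary analysis, so the point does not disappear.
- **The size rests on assumptions.** This also stands. The interval distribution, the independence of intervals and the equal drop-out are all assumed. Other assumptions give other shares: uniform intervals recorded in whole weeks give 3 of 9 combinations, or 33%. If 80% inject exactly on target and the rest uniformly over the window, the share is 0.2² × 0.5 = 2% for a 12-week target and 2 × 0.8 × 0.2 × 0.5 + 0.02 = 18% for a 13-week target. Reminders and the calendar may keep women close to their target, and nothing suggests clustering at the end of the window, so the 83% case is an outer illustration.
- **26 weeks is simply half a year.** That may explain the number, although the protocol does not say so. It does not remove the misclassification, and the 12-month outcome is not scored at week 52.
- **Another consistent rule exists.** Using 13 weeks for both cut-offs would give 26 and 39. That is uniform, but it would extend the same misclassification to the one-year outcome: a woman at 14-week intervals has injection 4 at week 42.
- **Previous Similar Studies is weak support.** Its remark that "no injections were given beyond the acceptable 14-week interval" describes an earlier non-randomized study, not this trial's rule. The finding does not need it, because the interval in Follow-Up Procedures is enough.

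**Conclusion.** The concern holds: the 6-month definition is wrong as written, because it scores some women who are on schedule as discontinued while the 12-month definition does not. This follows from the protocol's own interval and cut-offs and needs no assumption beyond injection 1 at enrollment.

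The size is uncertain. The power loss shown depends on the assumed interval distribution, independent intervals, equal drop-out per step and equal misclassification in both arms. Bias between arms would arise only if timing within the window differs by arm, which the documents do not suggest. Women whose first two intervals total 26 weeks or less are unaffected. The one-year outcome, the 338 completers and the 80% power all stand. The point should be fixed, but it does not threaten the trial's main result.

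**What to change.** Reconcile the outcome definition with Follow-Up Procedures by building both cut-offs from one rule: (number of injections − 1) × the upper limit of the stated interval. On the current text that gives 2 × 14 = 28 weeks for injection 3 and keeps 3 × 14 = 42 weeks for injection 4. This changes how the outcome is scored, not the injection schedule.

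Record injection dates in the 6-month survey if it does not already ask for them (the instruments are not in the text reviewed), and send it after the window for injection 3 has closed. State also that a repeat dose given after an uncertain injection counts once.

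The cost is one line in the outcome definition, at most one survey question, and possibly sending the survey up to two weeks later. No extra patients or visits are needed. Even with the corrected cut-off, power for the 6-month comparison would be about 68% under the assumptions above, so it should not be presented as a fully powered test.

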# **Secondary Hypotheses:**

Self-administration of DMPA sc is a feasible and satisfactory alternative to clinic administration of DMPA sc.

• Outcome variables: percent of patients able to successfully self-inject; participant satisfaction ratings with self-administration.

Self-administration of DMPA sc is cost effective compared to clinic administration of DMPA sc.

 Outcome variables: percent of dispensed DMPA sc used by participant; time and money spent on contracepting behaviors.

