## Study Drug Accountability

An accurate and current accounting of the dispensing and return of study drug for each subject will be maintained on an ongoing basis by a member of the study site staff. The number of doses dispensed (and/or returned) by the subject will be recorded on the Study Drug Accountability Log. The Research Coordinator will verify these documents throughout the course of the study.

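### The two outcome variables named for the cost-effectiveness hypothesis cannot support it; they can support a narrower comparison of patient costs plus self-arm drug wastage

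*Combined protocol and SAP*

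**What the plan says.** The Secondary Hypotheses section states: "Self-administration of DMPA sc is cost effective compared to clinic administration of DMPA sc". The outcome variables attached to it are "percent of dispensed DMPA sc used by participant; time and money spent on contracepting behaviors". The Secondary research questions ask about cost implications "for patients, providers, and payers". Objectives and Hypotheses is more modest: its objective is to compare costs of contraceptive care, and the listed outcome is cost differentials.

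Drug reaches the two arms differently. Under Study Procedures, self-arm women who inject correctly under supervision and want to go on at home are "provided medication (3 doses of DMPA sc), a self-administration kit" and instructions. The other arm "will be administered DMPA by qualified clinic personnel". Follow-Up Procedures adds: "Subjects will either return to the enrollment clinic or perform self-injection every 12–14 weeks, depending on study arm". No take-home stock is described for the clinic arm.

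Of the two variables, the Data Analysis section takes up only time and money, to be compared between groups. It does not mention the percentage of dispensed drug used.

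**The concern.** A claim of cost-effectiveness needs cost set against effect, from a stated perspective. Neither named variable does this. The percentage has a denominator that behaves differently by arm: a clinic dose seems to enter it only when it is injected, whereas a self-arm woman's three later doses enter it on the first day. Stopping early therefore lowers the score in one arm and leaves it unchanged in the other. The second variable, as described, is patients' own time and money, so it says nothing about providers or payers.

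The plan could thus lead to a cost-effectiveness statement that its data do not support. If the percentage were compared between arms, it could point against self-injection in a trial where self-injection had improved continuation. The Rationale says positive findings will change the organisation's medical standards, so an unsupported economic statement could carry weight.

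**Working it through.** The plan gives no figure for the cost hypothesis, so there is none to reproduce. Its sample-size figure, 338 completers, does reproduce (169 per arm, one-sided 5%, 80% power, pooled variance, no continuity correction). Only the two continuation rates behind it are used here.

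**Inputs from the protocol**
- 12-month continuation: 70% self, 57% clinic (Number of Subjects and Statistical Power).
- Self-arm doses: one supervised plus three taken home, so 4 dispensed (Study Procedures).
- A 12-month continuer has had 4 injections (Primary Hypothesis).

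**Inferred:** a clinic dose counts as dispensed when it is injected. The protocol never defines this; it follows from Study Procedures and Follow-Up Procedures.

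**Assumed, not in the protocol:** every self-arm woman takes three doses home; none crosses over; no syringe is spoiled; non-continuers use k doses, with k = 1, 2 or 3.

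**Formulas,** with p the continuation rate:
- Doses used per woman = 4p + k(1 − p)
- Self-arm percentage = doses used / 4
- Clinic-arm percentage = doses used / doses used = 100%

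| k | Self: doses used | Self: % of dispensed | Clinic: doses used | Clinic: % of dispensed | Gap in % (points) | Extra doses used, self | Unused per self-arm woman |
|---|---|---|---|---|---|---|---|
| 1 | 2.80 + 0.30 = 3.10 | 77.5 | 2.28 + 0.43 = 2.71 | about 100 | 22.5 | 0.39 | 0.90 |
| 2 | 2.80 + 0.60 = 3.40 | 85.0 | 2.28 + 0.86 = 3.14 | about 100 | 15.0 | 0.26 | 0.60 |
| 3 | 2.80 + 0.90 = 3.70 | 92.5 | 2.28 + 1.29 = 3.57 | about 100 | 7.5 | 0.13 | 0.30 |

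Stops spread evenly over doses 1 to 3 average k = 2, the middle row. In every row the self arm uses more doses and has the lower percentage.

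The gap does not need a difference in continuation. With 57% in both arms, the self arm would score 2.71/4 = 67.75%, 3.14/4 = 78.5% or 3.57/4 = 89.25%, against about 100%.

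**Cost against effect.** Three sections have to be read together. The hypothesis claims cost-effectiveness; the research question names three perspectives; the analysis section compares time and money only. Nothing in the text defines a cost per continuer, an incremental ratio, a net benefit or a source of unit costs, and no collection of provider or payer costs is described. The Summary says a year's drug supply was requested from the manufacturer for all participants. If it was granted, what patients spend will not reflect routine drug cost.

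**The case against.** The strongest reply is that the percentage was never meant to be compared between arms. Data Analysis does not list it among the between-group comparisons, and the companion feasibility hypothesis has outcome variables that apply to self-injection only. Reading the percentage as self-arm wastage is natural, and wastage is a real cost: an unused take-home dose is paid for by whoever supplies the drug, and dispensing at the visit avoids that cost. This stands. It removes the claim that the plan will show self-injection behind, but not the main point, because a wastage figure for one arm cannot establish cost-effectiveness relative to the other.

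A reader might infer that the percentage can only favour the clinic arm whatever the truth. The protocol does not support that. The arms tie if all take-home doses are used; women who cross over before taking doses home raise the self-arm figure when analysed as randomised; and the clinic figure of about 100% is itself inferred. Nor is a fixed 15-point deficit supported: it is one row of a range.

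A reader might also infer that nothing about cost can be answered. That goes too far. Patient time and money can be compared as planned, and if one arm both cost less and continued more, no ratio would be needed. That argument reaches only as far as the costs collected, which as described are the patients'.

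**Conclusion.** The concern holds in a limited form. The hypothesis of cost-effectiveness relative to clinic administration cannot be concluded from the two variables named for it. Used as a between-arm outcome, the percentage would put the self arm 7.5 to 22.5 points below a clinic arm fixed near 100%, while the self arm used 0.13 to 0.39 more doses per woman. Those sizes rest on the planned 70% and 57%, the assumptions listed with the calculation, and the inference about when clinic doses are dispensed. The between-arm use is itself conditional, since the protocol does not plan it explicitly.

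The planned data can still support a comparison of patient time and costs and an estimate of self-arm wastage. The provider and payer parts of the research question have no described data apart from what wastage contributes. The primary outcome and the sample size are unaffected.

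**What to change.** 1. Restate the hypothesis as a comparison of patient time and costs, in line with the cost differentials outcome. Confine the conclusion on the cost research question to patients plus drug wastage, unless provider and payer cost collection is added.
2. Do not use the percentage of dispensed drug as a between-arm outcome. Report doses used per woman randomised in both arms, and show doses dispensed but unused as a wastage cost of the self arm, not as a comparison with a clinic value that is zero by design. Analyse as randomised; Follow-Up Procedures places crossovers in the clinic group, whereas Data Analysis specifies intent-to-treat, so this needs stating.
3. Name the data sources. The accountability log alone is not enough: "The number of doses dispensed (and/or returned) by the subject will be recorded on the Study Drug Accountability Log". It does not record home injections, and the protocol text gives women no instruction to return unused doses. Self-reported injections are needed as well.
4. Optionally, report an incremental cost per additional 12-month continuer, with an interval, but only if a source of unit costs is specified, since the documents give none.

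Items 1 to 3 cost some wording, slightly more analysis and a narrower claim. Item 4 costs more, because prices must come from outside the trial.
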